Regardless of the fact that participants are withdrawn from treatment, every attempt will be made to follow up the participants unless they specifically request withdrawal from the trial.

6. Randomisation and Enrolment

Enrolment

Figure 3 below explains the recruitment and enrolment process for participants. Recruitment of participants will occur throughout various trusts in England and Scotland and participants will be referred to the 8 trusts running the REPOSE trial. A number of approaches will be used to inform potential participants about the trial and undertake recruitment. These are:

- 1. Details of the trial will be advertised through the use of the posters and leaflets in various clinics (diabetes outpatient, dietetic, general GP surgery).
- 2. Reception staff in diabetes clinics will be informed about the trial and will be provided with leaflets to give to patients who may express interest in the trial.
- 3. Various clinicians will provide information to patients and refer them to PIs to be screened and enrolled.
- 4. Participant identification centres (PIC) will be used at some research sites to assist in the identification of suitable participants

The leaflets and posters will provide brief details about the trial and contact numbers of study personnel (educators, PIs and the Trial Manager) for further information.

[figure not shown]
4. The PIs or educators (diabetes specialists who run the DAFNE courses) will identify participants from a DAFNE waiting list. They will then telephone individuals who are considered fit to participate.

[figure not shown]
Potential participants who are identified either through the DAFNE waiting list or by patients expressing an interest in the trial will be contacted by a study PI or educator. The PI or educator will give detailed information regarding the trial, and complete a check to assess that the participant fulfills all the inclusion and exclusion criteria listed above, either during a face-to-face or telephone consultation. Potential participants will then be offered a chance to attend a meeting for further information about the trial where informed consent may be obtained.

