Two analyses, one within the trial, and another using a lifetime analysis based on the Sheffield Type 1 Diabetes Policy Model (currently in development through the NIHR Programme Grant), will be undertaken. For the within trial analysis (and hence those parameters that will subsequently be used in the Policy Model), missing data will be imputed with multiple imputation within STATA using ICE. An incremental cost effectiveness ratio (ICER) will be calculated with uncertainty around this characterised by plots on the cost-effectiveness plane and its associated cost-effectiveness acceptability curve and frontier. Deterministic sensitivity analysis will examine the effect of calculating QALYs using the SF-6D as based on the SF12 data. Sub-group analyses will be undertaken using the same populations as used within the clinical analysis, namely, for participants with HbA1c level below and ≥7.5% (58mmol/mol).

Site & Trial Closure Procedures

At the point at which all questionnaires and CRF's have been collected and entered (or participants have failed to respond despite reminders) and all data have been entered and cleaned, closure of the database will be approved. The end of the trial is defined by the point at which all questionnaires are returned and entered (not at last patient last visit) since the participants may return questionnaires after the visit. Questionnaire data will make up a significant proportion of the trial data.

Trial Pharmacovigilance

The safety of trial participants is of utmost importance and as such MHRA legislation and Sheffield CTRU SOPs will be followed in order to conduct the trial safely and to be able to assess any adverse events or serious adverse events that may occur during the trial. The following section outlines the methods for ensuring and assessing participant safety:

Definitions

The Medicines for Human Use (Clinical Trials) Regulations 2004 (SI 2004/1031) definitions:

Adverse Event (AE)- Any untoward medical occurrence in a subject to whom a medicinal product has been administered, including occurrences which are not necessarily caused by or related to that product.

Serious Adverse Event (SAE), Serious Adverse Reaction (SAR) or Suspected Unexpected Serious Adverse Reaction (SUSAR)-Any adverse event, adverse reaction or unexpected adverse reaction, respectively, that:

- Results in death
- Is life-threatening* (subject at immediate risk of death)

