It is generally accepted that a difference of 0.5% in HbA1c is clinically worthwhile. To detect this difference with an SD of 1% at 80% power and 5% two sided significance using a t-test requires 64 patients per group for subjects \geq 7.5% (58mmol/mol) HbA1c. In order to allow for a clustering effect of the educators and a within-course intra-class correlation coefficient (ICC) of 0.05, which is common in diabetes care, the sample size increases to 84. Allowing also for a 10% drop out, the sample size per group becomes 93. Audit of the DAFNE database shows that 75% of subjects have an HbA1c of over 7.5% (58mmol/mol). With this in mind we require 124 subjects per group, i.e. 248 in total. We plan to recruit 280 subjects which increases the power to 85% but which allows for some variation in drop-out rates and the proportion of

patients with HbA1c ≥7.5% (58mmol/mol).

We believe that we should include patients who experience frequent hypoglycaemia but who might have existing levels of HbA1c that are near the target range since they may reduce hypoglycaemic episodes and can therefore still provide important information about quality of life. Yet, since there will be no change in HbA1c levels for these participants, including this data would reduce our statistical power to establish improvement in our primary endpoint. We will therefore stratify those entering the trial based on HbA1c levels of $\geq 7.5\%$ (58mmol/mol). The trial will be powered on the number of participants with an HbA1c $\geq 7.5\%$ (58mmol/mol), in whom a fall would reflect worthwhile improvements in glycaemic control but we will also calculate the number of participants in each group who achieve a HbA1c <7.5\% (58mmol/mol).

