In August 2012, a review of recruitment and retention to the trial took place. Recruitment to the trial was on target and most DAFNE courses were allocated with at least 7 participants (planned number of participants per course). However, a number of participant withdrawals (18 from 168 randomised) had also occurred post-randomisation but pre-DAFNE course delivery. The intention-to-treat population is participants who consent to take part in the trial **and** who attend their DAFNE course at least in part. As such participants recruited to the study who do not attend their DAFNE course do not count in the ITT population.

The study sample size of 280 participants allows for a $\leq 10\%$ drop-out rate during the year follow-up. The current rate of participant withdrawal which has occurred exclusively prior to DAFNE course delivery is 11% and the mean number of participants per course is 6. The trial statistician undertook a review to determine the need for additional courses to maintain the study power based on the current drop-out rate. Scenarios were modelled based on current and predicted HbA1c population prevalence ($\geq 7.5\%$) drop-out rate (10% or 15%) and size of

DAFNE course (4, 5, 6 or 7 participants). Assuming these variables remain similar to what has been currently observed (as of August 2012), the trial will need to run an additional two to seven courses in order to maintain power to determine the primary outcome.

Therefore, more than 280 participants will be recruited to the trial to replace participants who drop-out prior to attending their DAFNE course. The number of participants recruited will not exceed 340; however there will be no more than 280 in the ITT population.

As the last two course pairs run at a site, reserve participants who can step in to fill drop-out participant places should they occur on either of the last two courses to ensure these courses run with sufficient numbers of participants.

Data Analysis

An intention to treat analysis will be used primarily but the effect of switching to a per protocol analysis will also be explored.

Primary Analysis

The primary analysis will be a linear model of HbA1c at 2 years with baseline HbA1c as a covariate, (which will improve the power relative to the predicted power). Generalised estimating equations (GEE) will be used to control for clustering within course.

Secondary Analysis

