Linear models of insulin usage, body weight, lipids and proteinuria will also be analysed at 2 years with baseline measures as covariates. We will use Poisson regression (or a zero-inflated Poisson regression if necessary) on the number of hypoglycaemic episodes in 2 years, which should also have more power than an analysis based on dichotomy of having experienced/not experienced an episode. Again, GEE will be used for these analyses to account for clustering.

Subgroup Analyses

The analyses outlined above will also be completed for sub-groups stratified at baseline by participants with HbA1c level < and \geq 7.5% (58mmol/mol).

Primarily data will be analysed with missing data excluded. A secondary analysis will also be included using multiple imputation.

Quantitative Psychosocial Analysis

All variables will be subject to statistical analysis. Descriptive and inferential statistical analysis will be conducted using T-tests and ANOVA to compare means, crosstabs to explore individual variables, non-parametric tests including chi-square, correlational analysis and possibly multiple regression analysis. Statistical significance will be defined as $p \le 0.05$ with 95% confidence intervals.

Primarily data will be analysed with missing data excluded. Secondary analyses will also be completed with a) a mean score for each missing questionnaire and b) a minimum score for each missing questionnaire.

A full Statistical Analysis Plan will be submitted at a later date in order to detail this section of the protocol.

10. Trial Supervision

Three committees are being established to govern the conduct of the study:

- 1. Trial Management Group (TMG)
- Trial Steering Committee (TSC)
 Data Monitoring and Ethics Committee (DMEC)

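### The primary HbA1c analysis drops participants without a 2-year value although their 6- and 12-month HbA1c is collected; using those values is a cheap improvement

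*Protocol*

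**What the plan says.** The relevant statements are in section 9, Data Analysis. On the principle: "An intention to treat analysis will be used primarily but the effect of switching to a per protocol analysis will also be explored". On the model: "The primary analysis will be a linear model of HbA1c at 2 years with baseline HbA1c as a covariate", with generalised estimating equations (GEE) for clustering within course. On missing values: "Primarily data will be analysed with missing data excluded. A secondary analysis will also be included using multiple imputation". That last statement is printed under Subgroup Analyses, but it is worded generally, and no other rule covers the primary clinical analysis. The quantitative psychosocial analysis has a separate rule of its own.

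The Trial Summary and Table 1 schedule HbA1c at baseline, 6 months, 1 year and 2 years in both arms, and section 8 makes the central-laboratory result the primary measure.

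On people who leave treatment, section 5 says that "every attempt will be made to follow up the participants unless they specifically request withdrawal from the trial".

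**The concern.** The aim is an intention-to-treat comparison, but a single-time-point model with missing values excluded compares only those who supplied a 2-year sample. For someone lost after the course, the best available guide to the 2-year value is HbA1c at 12 months, or failing that at 6 months. The primary model has no place for either.

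The implied assumption is that, within an arm and at a given baseline HbA1c, those with and without a 2-year value have the same expected 2-year HbA1c. If that fails differently in the two arms, the primary estimate is shifted. Treatment is open, so a difference between arms is possible, but the protocol gives no evidence for one. What is at stake is a modest, avoidable dependence of the headline result on a strong assumption, and a little lost precision.

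**Working it through.** **1. The plan's own figures (section 9, Sample Size).** The difference is 0.5% ("It is generally accepted that a difference of 0.5% in HbA1c is clinically worthwhile") and the SD 1% ("To detect this difference with an SD of 1% at 80% power and 5% two sided significance"). A two-sample t-test needs 64 per group, as stated ("requires 64 patients per group for subjects"). With courses of 7 and an ICC of 0.05 the design effect is 1 + 6 × 0.05 = 1.30, and 64 × 1.30 = 83.2, rounded up to 84. Then 84/0.9 = 93.3 (stated 93), 93/0.75 = 124 per group, and 248 in total. For 280: 140 × 0.75 × 0.9 = 94.5 per arm, 94.5/1.30 = 72.7 effective, power about 85%. Everything reproduces, and nothing below changes the sample size.

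**2. Bias of the complete-case contrast.** In one arm let *d* be the share without a 2-year value and *g* the mean 2-year HbA1c of those missing minus that of those observed, given baseline. The observed mean equals the full mean minus *d* × *g*. The apparent CSII benefit (MDI minus CSII) is therefore off by

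*d*(CSII) × *g*(CSII) − *d*(MDI) × *g*(MDI).

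- Equal loss and equal gap in both arms: zero.
- CSII only, *d* = 0.10 and an assumed *g* = 0.5 (those lost had none of the benefit): 0.10 × 0.5 = 0.05 in favour of CSII. Completers show 0.50 where the whole group has 0.9 × 0.5 = 0.45.
- The same pattern in MDI only: 0.05 against CSII.

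**3. Simulation at 10% loss.** Loss after 12 months depends on 12-month HbA1c in CSII and is random in MDI. The mechanism and the between-visit correlations are assumptions, since the protocol gives neither.

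| Assumptions | Complete-case bias towards CSII | Using 6- and 12-month values |
|---|---|---|
| No true difference, SD 1%, equal correlations 0.5 to 0.7, log-odds of loss 1.5 per SD, no clustering | 0.032 to 0.036 | about 0.00 |
| True difference 0.5, SD 1%, ICC 0.05, 14 courses of 7 per arm, baseline correlation 0.5, follow-up correlations 0.6/0.7/0.8, log-odds about 1 per SD | 0.037 / 0.045 / 0.053 | within 0.005 of zero |

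The first row agrees with step 2: the simulated gap was about 0.35, and 0.10 × 0.35 = 0.035. Its type I error was about 6% against a nominal 5%. A rerun under the second row's assumptions gave about 0.04 to 0.06. Taken together the range is about 0.03 to 0.06. With the same HbA1c-dependent loss in both arms the bias was about zero.

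**4. Scale.** With 84 per group left after drop-out, design effect 1.30 and an assumed baseline correlation of 0.5, the standard error is √[(2 × 1.30/84) × (1 − 0.5²)] = 0.152. Then 0.03/0.152 = 0.2 and 0.06/0.152 = 0.4.

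**5. Precision.** Using the interim values changed the complete-case to interim-value variance ratio to 1.01 to 1.06 under CSII-only loss and 1.02 to 1.08 under equal loss.

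**6. Limit of the remedy.** Section 8, Lost to Follow-Up, counts as lost those who miss two follow-up visits including the 24-month one, so they also lack a 6- or a 12-month value. When the 12-month value was missing too, a bias of about 0.015 to 0.04 points remained.

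**The case against.** The strongest reply is that this only reorders analyses that are already prespecified. Multiple imputation is planned, a divergence from complete cases would be visible, and a fuller analysis plan may list the imputation variables. That stands as a limit on severity. It does not remove the point, because the protocol itself settles which analysis carries the primary conclusion.

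Several stronger readings are tempting and are not supported:

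- **That the result will favour CSII.** A reader might infer this from the section 5 triggers of sustained high glucose or more frequent hypoglycaemia. These are grounds for leaving treatment, after which follow-up continues. The two glycaemic triggers are worded for any participant. The remark in section 4 about drop-out and adherence is a general argument for qualitative work. Nothing shows loss of 2-year values differing by arm, and the bias could run either way.
- **That 15% loss should be assumed.** The August 2012 review modelled 10% and 15% in response to withdrawals that all preceded the course (18/168 = 10.7%). Those people are outside the protocol's ITT population and are replaced, so the figure says nothing about loss after the course.
- **That the economic analysis contradicts the clinical one.** There, "missing data will be imputed with multiple imputation within STATA using ICE". Costs and area-under-the-curve QALYs need complete data over several visits, so a different primary method is ordinary, and the clinical imputation analysis supplies a matching estimate.

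The protocol also limits missingness: home or alternative-site visits, data from medical records, and a second HbA1c sample measured locally. These help, though a telephone call cannot supply a blood result and a value from records is not the central-laboratory measure.

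**Conclusion.** The point holds as a cheap improvement. The primary HbA1c analysis is fixed as complete-case and leaves out information already collected on people without a 2-year value. It is unbiased only if missingness depends on arm and baseline HbA1c alone.

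The possible harm is modest and conditional: about 0.03 to 0.06 points at the planned 10% drop-out if only one arm loses people according to post-course HbA1c, and about zero if loss is similar in both. These sizes rest on an assumed loss mechanism and assumed correlations. The protocol supports neither a direction nor a loss above the planned 10% after the course. If missingness depends on the unobserved 2-year value itself, neither ordering removes the bias.

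**What to change.** State that the primary HbA1c analysis includes every participant in the primary population and uses the 6- and 12-month central-laboratory values, by one of two routes:

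- the multiple imputation already planned, done separately by arm, with baseline, 6- and 12-month HbA1c in the imputation model and allowance for course, followed by the stated baseline-adjusted GEE model; or
- a repeated-measures model of HbA1c at 6, 12 and 24 months with arm-by-visit terms, baseline HbA1c and course clustering, reporting the 24-month contrast.

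Keep the complete-case analysis as a sensitivity analysis.

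The cost is a change of wording and some extra analysis. No patients, visits or samples are added and the sample size stands. In return the assumption becomes missing at random given interim HbA1c, which is weaker than the present one, and precision improves slightly. The downside is that the primary result then depends on an imputation or longitudinal model, and the correction is only partial for participants who also lack a 12-month value.

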The aim of the study is to conduct an RCT comparing optimised MDI therapy (using rapid and twice daily long-acting insulin analogues) with CSII in adult type-1 diabetic patients provided with high quality structured education (Dose Adjustment for Normal Eating-DAFNE).

- 1) During the RCT the following measures will be assessed over 2 years:
 - a) biomedical outcomes (HbA1c, rates of hypoglycaemia, insulin dose, body weight, albumin-creatinine ratio),

b) quantitative and qualitative psychosocial outcomes (quality of life (generic and diabetes specific), treatment satisfaction, fear of hypoglycaemia, hypoglycaemia unawareness, self-efficacy, social support, adherence to treatment, emotional well-being, acceptability of technology),

c) adverse events (severe hypoglycaemia. hospital admissions with hypoglycaemia, diabetic ketoacidosis)

[figure not shown]
2) Through a combined analysis of the quantitative and qualitative measures we will identify factors which predict and/or help explain outcomes on CSII.

3) A cost effectiveness analysis will be undertaken to determine whether the marginal benefits of CSII over optimised MDI (if demonstrated) are commensurate with the marginal costs, as reflected in a cost per QALY acceptable to NICE.

3. Trial Design

REPOSE is a multi-centre parallel group, cluster randomised controlled trial, in which 280 adults with type-1 diabetes will be recruited from 7 trusts/Health Boards across the UK. The participants will be male or female above the age of 18 yrs. The participants will be allocated a place on a week-long DAFNE course depending on their availability. Prior to the course starting, the courses will be randomly allocated to be either CSII or MDI treatment. Participants will be requested to attend visits in order to obtain biochemical, psychosocial and health economic follow-up measures at baseline (i.e. after course allocation), 6 months, 1 year and 2 years after they have completed the DAFNE course. The diagram below gives an overview of the trial design.

Figure 1. Model of Trial Design

Primary Endpoints

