After consent, participants will be allocated to courses depending on their availability in relation to the dates of the courses. A computerised system will be used within Sheffield Clinical Trials Unit in order to randomise 48 DAFNE courses to either MDI or CSII courses across the 8 participating sites. The randomisation for courses will be stratified by site. Within each centre the first four courses will be randomised in pairs (one MDI, one CSII). The remaining courses will be randomised by minimisation. PIs/Educators will attempt to have allocated 7 individuals to each course at least six weeks prior to the course commencing. By this time, the CTRU will inform the centre whether the course has been allocated as a CSII course or as an MDI course and confirm the allocation of a course number. The PIs and educators will have been blinded to the type of course being delivered until four to six weeks before the course commences and staff within the trials unit will be blinded to the identity of those participating. The participant will find out which course they are allocated to four weeks prior to the DAFNE course. Once the course number has been allocated to the course and the type of course is known to the site, further participants will only be allocated to the course in the situation described below.

If for any reason participants are unable to take part in the course at short notice, they will only be able to participate in the same arm of the study as the course they were originally allocated to. The patient will be given possible dates for the next relevant course and will be informed when that course is due to commence as soon as the PI/educator finds out.

In order to maximise recruitment for the courses, the PI's and educators will be able to invite a new participant to take the place of somebody unable at attend. This will occur only where there is a list of reserve participants in place, prior to the time when the course allocation has been revealed to the educators. In this case, the next person on that list would be invited to participate in that arm of the study. The patient will be allocated a screening number at the point at which they have been invited to participate and have had the inclusion/exclusion criteria check. This screening number will be used to assess the next person on the list.

7. Trial Treatment

Insulin

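### The psychosocial analysis names tests that treat participants as independent, although courses are randomised and the other outcome analyses allow for clustering by course

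*Protocol*

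**What the plan says.** Section 3 (Trial Design) states the design: "REPOSE is a multi-centre parallel group, cluster randomised controlled trial". Under Randomisation in section 6, a computer system is to "randomise 48 DAFNE courses to either MDI or CSII courses across the 8 participating sites", so the course is the unit of allocation.

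Section 9 carries this through for the clinical outcomes. The Sample Size text enlarges the HbA1c sample "In order to allow for a clustering effect of the educators and a within-course intra-class correlation coefficient (ICC) of 0.05", and the severe-hypoglycaemia power statement allows for the same ICC. The Primary Analysis is a linear model of 2-year HbA1c with baseline as covariate and GEE for course. The Secondary Analysis covers insulin usage, weight, lipids, proteinuria and hypoglycaemia counts, and ends: "Again, GEE will be used for these analyses to account for clustering".

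The Quantitative Psychosocial Analysis paragraph comes later under its own heading. It says: "Descriptive and inferential statistical analysis will be conducted using T-tests and ANOVA to compare means". It adds crosstabs, chi-square, correlation and, as a possibility only, multiple regression. The significance threshold is p ≤ 0.05 with 95% confidence intervals. Neither a course term nor a baseline covariate is named. A fuller statistical analysis plan is promised afterwards.

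**The concern.** Section 4 gives comparison of the arms on quality of life and other psychological outcomes as a purpose of the psychosocial study, and section 9 calls the analysis inferential. A t-test, one-way ANOVA or chi-square test assumes independent participants. Here people are allocated together and taught together for five days by the same educators, so scores within a course may be correlated. If they are, the standard error of the between-arm difference is too small, intervals are too narrow and chance differences reach p ≤ 0.05 too often.

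The GEE sentence does not reach this paragraph. It closes the Secondary Analysis text and refers to the analyses listed there. Section 8 also describes a separate route for these data: the psychosocial researcher extracts and analyses them in SPSS, and clustering is not mentioned.

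A second, distinct matter is baseline. Table 1 shows most instruments being given at baseline, yet the psychosocial paragraph does not name the baseline score as a covariate, as the HbA1c and continuous biomedical models do.

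**Working it through.** **Inputs.**
- ICC 0.05: "within-course intra-class correlation coefficient (ICC) of 0.05, which is common in diabetes care, the sample size increases to 84" (Sample Size). It is given for HbA1c and reused for severe hypoglycaemia; none is given for questionnaire scores.
- Course size m: 7 planned; in the August 2012 review, "the mean number of participants per course is 6". As a check, 280 / 48 = 5.8.
- Test level: 5% two-sided.

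**Reproducing the protocol's own figures.** The design effect is DE = 1 + (m − 1) × ICC. With m = 7, DE = 1 + 6 × 0.05 = 1.30.
- Two-sample t-test, difference 0.5, SD 1, 80% power: 63.8, so 64 per group, as stated.
- 64 × 1.30 = 83.2, so 84, as stated.
- 84 / 0.9 = 93.3 (93 stated); 93 / 0.75 = 124, as stated.
- At 280 recruited: 140 × 0.75 × 0.9 / 1.30 = 72.7 effective per arm, power 0.849 (85% stated).

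The protocol therefore used DE = 1.30, and the same formula can be applied to the psychosocial tests.

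**Effect of ignoring course.** The naive standard error is too small by a factor √DE. The true two-sided error is 2 × [1 − Φ(1.96 / √DE)], and the naive interval has 1/√DE of the correct width.
- m = 6, ICC 0.05: DE = 1.25; 1.96 / √1.25 = 1.753; error 8.0%; coverage 92.0%; width ratio 0.894.
- m = 7, ICC 0.05: DE = 1.30; 1.96 / √1.30 = 1.719; error 8.6%; coverage 91.4%; width ratio 0.877.

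A simulation of an ordinary t-test on course-randomised data (20,000 runs per setting) agreed: 8.1% for m = 6 with 24 courses per arm, and 8.4% for m = 7 with 20 per arm.

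**Range over assumed ICCs for questionnaire scores.**

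| Assumed ICC | True error, m = 6 | True error, m = 7 |
|---|---|---|
| 0 | 5.0% | 5.0% |
| 0.01 | 5.6% | 5.7% |
| 0.02 | 6.2% | 6.4% |
| 0.05 | 8.0% | 8.6% |
| 0.10 | 11.0% | 12.1% |

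If missing questionnaires reduced the analysed course size to 5, the figure at ICC 0.05 would be 7.4% (DE = 1.20; simulated 7.1%).

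**Baseline.** If a baseline score has correlation r with follow-up, adjusting for it multiplies the residual variance by 1 − r². Omitting it widens the interval by 1/√(1 − r²): 1.05, 1.15 and 1.40 for assumed r of 0.3, 0.5 and 0.7. This acts in the opposite direction to the clustering error and does not raise the false-positive rate.

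**The case against.** The strongest reply is that the paragraph is a loose menu. It mixes description, exploration and inference, fixes no definitive between-arm test or time point, and is followed by the promise of a detailed analysis plan that is not shown here. A reader might infer that the trial's final analysis will ignore clustering; the protocol does not establish that. What stands is narrower. The protocol names particular inferential tests with a significance threshold, and those tests do not fit its own design. A later plan that details them faithfully inherits the problem, and one that corrects them departs from the protocol.

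The size is also open to challenge, and fairly. The ICC of 0.05 belongs to other outcomes; at 0.01–0.02 the inflation is small, and course sizes below 7 reduce it further. The figures above are therefore conditional.

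Three stronger readings should be resisted.
- That omitting baseline scores also makes intervals too narrow. It does not; the cost is lost precision and uncorrected chance imbalance. Nor does the text exclude baseline: the study is described as longitudinal with repeated measures, the form of ANOVA is undefined, and regression remains possible.
- That a pump benefit is most likely to be claimed on these outcomes. The protocol lists them as ancillary endpoints and says they will help interpret the findings.
- That the number of scales and visits makes the inflation worse. Multiplicity is a separate question and has not been quantified here.

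**Conclusion.** The point holds as an inconsistency in the text. Inference on psychosocial outcomes is assigned to individual-level tests in a course-randomised trial whose sample size and other stated outcome analyses allow for course.

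Under the protocol's only ICC, borrowed for questionnaire scores as an assumption, using those tests as named would put the true error at about 8.0–8.6% instead of 5%, with intervals 11–12% too narrow. Across assumed ICCs from 0.01 to 0.10 the true error runs from about 5.6% to 12.1%. Confidence is high in the inconsistency and lower in any single figure.

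The missing baseline covariate is an efficiency point only. This should be fixed, but it does not threaten the trial's main result: the HbA1c and biomedical analyses already allow for course.

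**What to change.** Amend the Quantitative Psychosocial Analysis paragraph, and carry the same wording into the analysis plan, to state that:
- between-arm comparisons of questionnaire scores will use the course-level GEE already specified for the clinical outcomes, or a mixed model with course as a random effect; with about 24 courses per arm (48 / 2), a small-sample correction to the GEE standard errors is sensible;
- categorical outcomes will use the logistic equivalent;
- the baseline score will be a covariate where the same instrument was given at baseline, which excludes the change-version DTSQ at 1 year and the three questionnaires added only at 2 years;
- t-tests, ANOVA, chi-square and crosstabs are for description only.

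Site terms or a joint model over visits could be considered, but the stated clinical models do not name them and this correction does not need them.

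The cost is a wording change and a little programming. At ICC 0.05, allowing for course widens intervals by √1.25 = 1.12 to √1.30 = 1.14; baseline adjustment would recover some or all of that, depending on r.
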